### **8.1.3 Clinical Safety Laboratory Assessments**

Blood and urine samples for determination of clinical chemistry, haematology, and urinalysis will be collected at screening and at EOS (Day 168±7) as indicated in the SoA.

Clinical chemistry will include serum alkaline phosphatase, alanine aminotransferase, aspartate aminotransferase, gamma glutamyl transferase, lactate dehydrogenase, total protein, total bilirubin, albumin, and serum creatinine. Haematology will include haematocrit, leucocyte count, leucocyte differential count (absolute count), platelet count, and haemoglobin. Urinalysis (dipstick) will assess urine haemoglobin/erythrocytes/blood, protein/albumin, and glucose.

Additional safety samples may be collected if clinically indicated at the discretion of the investigator. The date, time of collection, and results (values, units, and reference ranges) will be recorded on the appropriate eCRF.

The clinical chemistry, haematology, and urinalysis will be performed at a local laboratory at or near the investigator site. Sample tubes may vary depending on laboratory method used and routine practice at the site.

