## 9.4.3 Effectiveness

In order to assess effectiveness of benralizumab in participants of severe asthma of eosinophilic phenotype, following results will be presented using Evaluable Analysis Set:

Annualised exacerbation rate per 24-week period will be reported as percentage, and 95% CI (exact Poisson method), and will be presented in the SAP.

The proportion of participants with  $\geq 1$  asthma exacerbation during the study period will be described using the frequency and the percentage. The proportion of such participants will be calculated as: (number of participants with  $\geq 1$  asthma exacerbation during the 24 week study period)/(total number of participants in the study).

Overall investigator's assessment on the outcome of study treatment will be summarised using frequency and percentage.

Time from first dose of study treatment to the first asthma exacerbation will be calculated as follows: Start Date of first asthma exacerbation minus Date of first dose of study treatment plus 1. The time to first asthma exacerbation for participants who do not experience an asthma exacerbation during the study period will be censored at 24 weeks, or at the time point after which an exacerbation could not be assessed (for lost-to-follow-up participants). The data will be summarised through median time to the first asthma exacerbation along with the 95% CI of median (as per availability of data) and displayed graphically using a KM plot.

The absolute values of blood eosinophil levels and the change from baseline at Week 4, Week 16, and Week 24 will be summarised descriptively using number of observations, arithmetic mean, SD, median, 25th and 75th percentiles, and minimum and maximum values.

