6.3.2 Secondary Endpoint Analysis

All Secodary Endpoints will be summarized based on the Evaluable Analysis Set.

Descriptive summaries will be provided for the Asthma Exacerbation. All the continuous variables will be summarized by n, mean, standard deviation, minimum, median and maximum values. All the categorical variables will be summarized as frequency, percentage of Patients in each category and corresponding 95% CI (using Clopper-Pearson exact Method, where appropriate).

Time from first dose of study treatment to the first asthma exacerbation will be calculated as follows: Start Date of first asthma exacerbation minus Date of first dose of study treatment plus 1. The time to first asthma exacerbation for participants who do not experience an asthma exacerbation during the study period will be censored at 24 weeks, or at the time point after which an exacerbation could not be assessed (for lost-to-follow-up participants). The data will be summarised through median time to the first asthma exacerbation along with the 95% CI of median (as per availability of data) and displayed graphically using a KM plot.

Blood Eosinophils level will be summarized based on the Evaluable Analysis Set.

Blood Eosinophils will be summarised descriptively for actual values and change from baseline at week 4, 16, 24 using the number of observations, arithmetic mean, SD, median, 25th and 75th percentiles, and minimum and maximum values.

The Blood Eosinophils in this study is to evaluate the change from baseline to Post-baseline will be analysed using Paired t – test / Wilcoxon signed-rank test at 5% level of significance.

Change from baseline will be determined as:

Change from Baseline = (Post-baseline – Baseline)

Percent Change Change from Baseline = ([Post-baseline – Baseline] / Baseline) X 100

Overall Investigators Assessment will be summarized based on the Evaluable Analysis Set.

Descriptive summaries will be provided for the Overall Investigators Assessment.

Document Title:	Document ID:	BP04-01
Statistical Analysis Plan	Version Number:	3.1
	Effective Date:	25-Nov-2021

All the categorical variables will be summarized as frequency, percentage of Patients in each category and corresponding 95% CI (using Clopper-Pearson exact Method, where appropriate).

7. References

1. ICH E3 Guideline_International Council for Harmonisation

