No	xx (xx.xx)	(xx.xx, xx.xx)
Missing	xx (xx.xx)	(xx.xx, xx.xx)
Visit x		
Patient Experience any new Exacerbation or change in existing Exacerbation since last visit		
Yes	xx (xx.xx)	(xx.xx, xx.xx)
No	xx (xx.xx)	(xx.xx, xx.xx)
Missing	xx (xx.xx)	(xx.xx, xx.xx)

- The Capital "N" in the column header represents the total number of Evaluable Analysis Set.
- The small "n" in summary statistics represents the total number of patients.
- All Percentages rows are based on the total number of Evaluable Analysis Set.
- 95% CI calculate will be using Clopper-Pearson Exact method.
- Programmer Note: Visit x- Visit 2, Visit 3, Visit 4 and Visit 5
- Source: Listing 16.2.1.1 and Listing 16.2.1.2

Document Title:	Document ID:	BP04-01
Statistical Analysis Plan	Version Number:	3.1
	Effective Date:	25-Nov-2021

Table 14.2.1.3. Summary of Before and After Treatment Exacerbation (Evaluable Analysis Set)

N = xx

**Exacerbation
before study**

N	xx
Missing	xx
Mean (SD)	x.x (x.xx)
Median	x.x
(min, max)	(x,x)
(25th Percentile, 75th Percentile)	(x.xx, x.xx)

**Exacerbation at
end of study**

n	xx
Missing	xx
Mean (SD)	x.x (x.xx)
Median	x.x
(min, max)	(x,x)
(25th Percentile, 75th Percentile)	(x.xx, x.xx)
P-value	x.XXXX

**Annualized
exacerbation
rate**

x.xx

- The column header's capital "N" denotes the total number of Evaluable Analysis Sets.
- The modest "n" in the number of patients suffering from exacerbation.
- The annual rate for each patient was calculated by dividing the total number of exacerbations by the number of days participated in the study and multiplying by 365.
- Source: Listing 16.2.2.1, Listing 16.2.2.2 and Listing 16.2.2.3

Document Title:	Document ID:	BP04-01
Statistical Analysis Plan	Version Number:	3.1
	Effective Date:	25-Nov-2021

Table 14.2.2. Summary of Time to first Exacerbation (Evaluable Analysis Set)

		N=xxx
Patient Asthma Exacerbation, n (%)		
Yes		xx(xx.xx)
No		xx(xx.xx)
Duration of Patient First Asthma Exacerbation (Days)		
n		Xx
missing		xx
Mean (SD)		xx.x (xx.xx)
Median		xx.x
(min , max)		(xx.xx, xx.xx)
(25 th Percentile, 75 th Percentile)		(xx.xx, xx.xx)
Estimate for Time to Response (Days)		
Median		xx.x
95 % CI		(xx.xx, xx.xx)

- The Capital "N" in the column header represents the total number of Evaluable Analysis Set.
- The small "n" in summary statistics represents the total number of patients
- Estimate for Time to Response using Kaplan-Meier method.

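### Table 14.2.1.3 takes its end-of-study mean over patients who had an exacerbation, and the SAP leaves the denominator of the annualised rate undefined

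*SAP*

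**What the plan says.** SAP section 8, Table 14.2.1.3, is titled for the Evaluable Analysis Set. Its footnote says that capital *N* in the column header "denotes the total number of Evaluable Analysis Sets". The count row of the before-study block is labelled *N*. The count row of the end-of-study block is labelled *n*, which the footnote defines with the words "in the number of patients suffering from exacerbation" (the opening word is presumably a slip for *is*). Each block then lists a Missing row, mean (SD), median, range and quartiles. The end-of-study block adds a P-value, and a single cell for the annualised exacerbation rate follows.

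The rate has one footnote: "The annual rate for each patient was calculated by dividing the total number of exacerbations by the number of days participated in the study", the result being multiplied by 365. The data source is given as "Source: Listing 16.2.2.1, Listing 16.2.2.2 and Listing 16.2.2.3". These listings record individual exacerbations.

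Elsewhere, SAP 6.3.2 says that all secondary endpoints "will be summarized based on the Evaluable Analysis Set", but it describes no method for the annualised rate. Protocol 9.4.3 introduces effectiveness with "following results will be presented using Evaluable Analysis Set" and asks for an exact Poisson interval: "Annualised exacerbation rate per 24-week period will be reported as percentage, and 95% CI (exact Poisson method"). It leaves the presentation to the SAP. SAP section 1 adds that where the two documents differ, the SAP prevails.

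**The concern.** A mean count over patients who had at least one event answers a different question from a mean count over everyone treated. It says how many exacerbations a patient had, given that there was one. It hardly reflects how many patients stayed free of exacerbations, which is most of what a reader wants from a before-and-after table.

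If the before block covers all Evaluable patients and the end-of-study block only those with an event, the two columns of statistics describe different groups, and a P-value between them has no clear meaning.

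The annualised rate is a named secondary endpoint, and this shell is the only place in the available SAP text that says how to compute it. The footnote gives a rate per patient. It does not say which patients enter the single printed figure, or whether that figure is a mean of patient rates or a pooled rate.

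**Working it through.** The plan states no figure to reproduce here, since the cells of the shell are placeholders. The check has three parts.

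**1. Is the wording of *n* specific to this table?** The shells for Tables 14.1.2.2, 14.2.1.1, 14.2.2 and 14.2.3 define small *n* simply as a count of patients. Table 14.2.2 does so while citing the same three listings. The restriction to patients with an exacerbation is therefore peculiar to Table 14.2.1.3. Under it, a patient without an event has no defined place in the end-of-study block: either omitted or counted as Missing.

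**2. Size of the effect on the mean count.** Inputs: 168 days of follow-up (24 weeks, protocol 4.1), and true rates of 0.25, 0.5 and 1.0 per year, which are assumed because the documents give none. With Poisson counts:

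- mean over all patients: μ = rate × 168/365
- share with at least one event: p = 1 − exp(−μ)
- mean over patients with an event: μ/p

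| Assumed rate per year | μ (all patients) | p | μ/p (as the footnote reads) | Overstatement, 1/p |
|---|---|---|---|---|
| 0.25 | 0.115 | 0.109 | 1.059 | 9.2-fold |
| 0.5 | 0.230 | 0.206 | 1.119 | 4.9-fold |
| 1.0 | 0.460 | 0.369 | 1.248 | 2.7-fold |

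The true mean rises fourfold from the first row to the last. The printed mean rises by 1.248/1.059 = 1.18, or 18%. As p is below one half in every row, the median over all patients is 0, whereas over patients with an event it cannot be below 1.

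If counts vary more than Poisson (negative binomial with an assumed dispersion of 1), the restricted mean is 1 + μ, giving 1.12, 1.23 and 1.46. The picture is the same.

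**3. What would follow for the annualised rate, if it used the same *n*.** Each included patient would have at least one event, so the smallest patient rate is 365 divided by the days of follow-up. Protocol 8.1.3 places the final laboratory samples "at EOS (Day 168±7"), that is 161 to 175 days. Protocol 8.3.1 counts follow-up from enrolment, which protocol section 5 ties to consent, and Table 1 allows up to 14 days of screening before Day 1.

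- 365/161 = 2.27
- 365/168 = 2.17
- 365/175 = 2.09
- 365/182 = 2.01 (168 days plus 14 of screening)
- 365/189 = 1.93 (175 days plus 14 of screening)

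The conditional floor is thus about 1.9 to 2.3 per year for fully followed patients. A patient with an event who left early would have a higher rate still.

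To show the two readings side by side, take the 138 patients that the footnote to SAP Table 14.1.1.1 gives for the analysis set, each followed for 168 days, and suppose one event in each of *k* patients:

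- all 138 patients: (*k*/138) × 365/168 = 0.16, 0.31 and 0.63 per year for *k* = 10, 20 and 40
- patients with an event only: 1 × 365/168 = 2.17 per year in all three cases

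**The case against.** The best defence is that the footnote is bad drafting and nobody intends the restriction. It is ungrammatical, letter case varies across the shells, and the definition of capital *N* refers to the column header rather than to the row label in the before block. The table title and SAP 6.3.2 state the right population. This has weight: a slip is quite possible, and the contrast between *N* and *n* as row labels proves little alone. But the definition of *n* is explicit, differs from comparable shells, and sits on the rows from which a programmer works. Because the SAP overrides the protocol where they differ, protocol 9.4.3 cannot be relied on to correct it.

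A reader might go further and infer that patients without an event also drop out of the annualised rate, so that it cannot fall below about 2.1 per year. The documents do not support that as a statement of fact. The rate row carries no *n*, and a rate computed patient by patient can include zeros. Nor do the source listings settle it: Table 14.2.2 cites the same three, yet its Kaplan-Meier estimate needs patients without an event as censored observations. Those listings also hold no days of participation, so the rate could not be computed from them alone. Finally, 2.1 depends on counting days from Day 1; from consent, the floor drops to 1.93.

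It is also fair to say that this is a descriptive secondary endpoint in a single-arm safety study with no hypothesis (protocol 9.1, SAP 6.2), and that Table 14.2.2 already counts patients with and without an exacerbation. The shell for Table 14.2.1.2 is not in the text available, so whether it offers a further summary cannot be judged.

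**Conclusion.** The point holds for the end-of-study count. As written, its mean, SD, median and percentiles are conditional on having an event, the mean cannot be below 1, and the definition conflicts with the population in the table title, SAP 6.3.2 and protocol 9.4.3. At the assumed rates, the printed mean would be roughly 3 to 9 times the mean over all patients. That range rests on Poisson counts, 168 days and rates that the documents do not supply; the lower limit of 1 rests on none of these.

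For the annualised rate, the finding is an omission: no denominator and no rule for combining patients. A floor of about 1.9 to 2.3 per year is what would follow from reusing the same *n*, and should be read only as that. It does show why the gap matters, because protocol inclusion criterion 4 requires at least 2 exacerbations in the preceding 12 months. On the restricted reading the rate could hardly fall below that entry minimum, whatever happened on treatment.

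This should be fixed, but it does not touch the primary safety analysis.

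**What to change.** In Table 14.2.1.3:

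- Define *n* in the end-of-study block as all Evaluable patients with post-dose follow-up, and enter a count of 0 for those without an exacerbation. Keep Missing for patients whose exacerbation status is unknown.
- Use the same patients for the before and end-of-study statistics and for any P-value between them.
- Define the annualised rate as total exacerbations divided by total follow-up time over all these patients, expressed per patient-year, with the exact Poisson 95% interval named in protocol 9.4.3. State this in SAP 6.3.2 as well.
- State whether days run from Day 1 or from consent.
- Add as sources the listings that identify patients without an event and their follow-up (16.2.1.2 for visit-level status, 16.1.1.3 for completion dates, 16.1.6.1 for first dose).
- Cross-refer to Table 14.2.2 for the number of patients with an exacerbation.

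The cost is an edit to one shell and a short addition to SAP 6.3.2. No new data are needed.

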**Table 1 Schedule of Activities**

Procedure	Screening (Up to 14 Days Before Day 1)	Intervention Period				Follow-up EOS Week 24
		Day 1	Week 4	Week 8	(Last Dose) Week 16	
Visit		1	2	3	4	5
Informed consent	X					
Inclusion and exclusion criteria a	X					
Demography, anthropometry including BMI	X					
Significant medical history	X					
Clinical safety laboratory assessments b	X					X
Serum/urine pregnancy test (WOCBP only) c	X	X	X	X	X	X
Vital signs d	X	X	X	X	X	X
ECG	X		X			X
Targeted physical examination	X	X	X	X	X	X
Blood eosinophil count	X		X		X	X
Prebronchodilator FEV1	X					
Postbronchodilator FEV1 e	X					
Administration of benralizumab		X	X	X	X	
Recording Use of concomitant asthma medication (OCS/ICS/LABA)	X	X	X	X	X	X
Adverse events and Serious adverse events f (reported g and observed)	X	X	X	X	X	X
Assessment of asthma exacerbations	X	X	X	X	X	X

Abbreviations: BMI = body mass index; EOS = end of study; ECG= Electrocardiogram; FEV1 = forced expiratory volume in one second; ICS = inhaled corticosteroid; LABA = long-acting beta-agonist; OCS = oral corticosteroid; UPT = urine pregnancy test; WOCBP = women of childbearing potential (after menarche)

Version: 1.0 Dated 09 Mar 2021

a Recheck clinical status before first dose of benralizumab.

b Clinical safety laboratory assessment will include clinical chemistry, haematology, and urinalysis. Clinical chemistry will include serum alkaline phosphatase, alanine aminotransferase, aspartate aminotransferase, gamma-glutamyl transferase, lactate dehydrogenase, total protein, total bilirubin, albumin, and serum creatinine. Haematology will include haematocrit, leucocyte count, leucocyte differential count (absolute count), platelet count, and haemoglobin. Urinalysis (dipstick) will assess urine haemoglobin/erythrocytes/blood, protein/albumin, and glucose.

c Serum pregnancy test will be done at baseline and UPT will be done at Day 1, Week 4, 8, 16, 24.

d The vital signs (pulse, blood pressure, respiration rate, and body temperature) will be taken before benralizumab administration, and, if possible, blood drawing and usual asthma controller medication. If it is not logically possible, sufficient time as per clinician discretion should be allotted between phlebotomy and vital signs assessment. For details, please refer to [Section 8.1.3](#).

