#### 8.1.2 Vital Signs

Vital signs (pulse, blood pressure, respiration rate, and body temperature) and electrocardiogram

The vital signs will be taken before benralizumab administration, and, if possible, blood drawing and usual asthma controller medication.

Any new finding(s) or aggravated existing finding(s), judged as clinically significant by the investigator, will be reported as an AE as described in [Section 8.2.2](#) and [Section 8.2.3](#).

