### **9.4.1 General Considerations**

Statistical analyses will be primarily descriptive in nature. All tabulations, figures, and listings will be produced using the Statistical Analysis Software (SAS) System (Version 9.2 or higher). Data from all participating sites will be pooled for analysis. Standard method of imputation will be applied for any missing/ partial dates.

According to the objectives, the relevant parameters will be summarised descriptively with appropriate statistical methods: categorical variables will be presented using frequencies, percentages and corresponding 95% CI (using Clopper-Pearson exact method, where appropriate) and continuous variables using number of observations, arithmetic mean, standard deviation (SD), median, 25th and 75th percentiles, and minimum and maximum values. The last measurement prior to first dose of study treatment will serve as the baseline measurement.

The safety parameters including AEs, SAEs, deaths, treatment discontinuation/modification, patient discontinuation, laboratory data, etc. will be reported using safety analysis set.

The time-to-event endpoint will be summarised using Kaplan-Meier (KM) method along with the corresponding 95% CIs (as appropriate) and the KM curve will be plotted.

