- n = number of Patients in row category; E = number of serious TEAE
- TEAE are those adverse events which occurred after first dose of study medication.
- All Percentages rows are based on the total number of patients in the Safety Analysis Set.
- System Organ classes was sorted by descending frequency. Preferred terms are sorted by descending frequency within system organ class.
- Adverse events were coded using MedDRA version 24.1 If a patient has multiple occurrences of an AE, the patient is presented only once in the respective patient count column (n) for the corresponding AE. Events are counted each time in the event € column.
- Source: Listing 16.3.1.2, Listing 16.3.2.1 and Listing 16.3.2.2

Document Title:	Document ID:	BP04-01
Statistical Analysis Plan	Version Number:	3.1
	Effective Date:	25-Nov-2021

Table 14.3.3. Analysis of change in Vital Sign parameters from baseline to Visit 1, Visit 2, Visit 3, Visit 4 and Visit 5 (Safety Analysis Set)

	Observed value (N = xx)	Change from Baseline (N = xx)	% Change from Baseline (N = xx)
Vital Sign parameter x			
Baseline (Screening Visit)			
n	xx		
Missing	xx		
Mean (SD)	xx.x (xx.xx)		
Median	xx.x		
(min, max)	(xx.xx, xx.xx)		
(25 th percentiles, 75 th percentiles)	(xx.xx, xx.xx)		
Visit x			
n	Xx	Xx	xx
Missing	Xx	Xx	Xx
Mean (SD)	xx.x (xx.xx)	xx.x (xx.xx)	xx.x (xx.xx)
Median	xx.x	xx.x	xx.x
(min, max)	(xx.xx, xx.xx)	(xx.xx, xx.xx)	(xx.xx, xx.xx)
(25 th percentiles, 75 th percentiles)	(xx.xx, xx.xx)	(xx.xx, xx.xx)	(xx.xx, xx.xx)
p-value		x.XXX	x.XXX

- The Capital "N" in the column header represents the total number of patients in Safety Analysis Set.
- The small "n" in summary statistics represents the total number of patients.
- SD = Standard deviation, min=minimum, max=maximum
- Change from Baseline= Post-Baseline – Baseline
- % Change from Baseline = (Post-Baseline – Baseline / Baseline) X 100
- p-value calculate using paired t – test.
- Programmer Note: Vital Signs parameter x: Pulse rate (beats/min), Respiratory rate (breaths/min), Systolic blood pressure (mmHg), Diastolic blood pressure (mmHg) and Temperature(⁰F).
- Programmer Note: Visit x: Visit 1, Visit 2, Visit 3, Visit 4 and Visit 5
- Source: Listing 16.3.4

Document Title:	Document ID:	BP04-01
Statistical Analysis Plan	Version Number:	3.1
	Effective Date:	25-Nov-2021

(25th percentiles, 75th percentiles)

(xx.xx, xx.xx)

- The Capital "N" in the column header represents the total number of patients in Safety Analysis Set.

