- The small "n" in summary statistics represents the total number of patients.
- Percentages are based on number of Safety Analysis Set.
- SD = Standard Deviation, min=minimum, max=maximum
- Programmer Note: Visit x: Screening Visit, Visit 2 and Visit 5
- Source: Listing 16.3.5

Document Title:	Document ID:	BP04-01
Statistical Analysis Plan	Version Number:	3.1
	Effective Date:	25-Nov-2021

Table 14.3.5. Summary of Targeted Physical Examination (Safety Analysis Set)

	N = xx
	n (%)
Visit x	
Physical Examination Performed	
Yes	xx (xx.xx)
No	xx (xx.xx)
General Appearance	
Normal	xx (xx.xx)
Abnormal	xx (xx.xx)
If Abnormal	
Abnormal CS	xx (xx.xx)
Abnormal NCS	xx (xx.xx)
Respiratory System	
Normal	xx (xx.xx)
Abnormal	xx (xx.xx)
If Abnormal	
Abnormal CS	xx (xx.xx)
Abnormal NCS	xx (xx.xx)
Cardiovascular System	
Normal	xx (xx.xx)
Abnormal	xx (xx.xx)
If Abnormal	
Abnormal CS	xx (xx.xx)
Abnormal NCS	xx (xx.xx)
Abdomen	
Normal	xx (xx.xx)
Abnormal	xx (xx.xx)
If Abnormal	
Abnormal CS	xx (xx.xx)
Abnormal NCS	xx (xx.xx)
Skin	
Normal	xx (xx.xx)
Abnormal	xx (xx.xx)
If Abnormal	
Abnormal CS	xx (xx.xx)
Abnormal NCS	xx (xx.xx)
Head, Eye, Ear, Nose, Throat	
Normal	xx (xx.xx)
Abnormal	xx (xx.xx)
If Abnormal	
Abnormal CS	xx (xx.xx)
Abnormal NCS	xx (xx.xx)
Lymph Node	
Normal	xx (xx.xx)
Abnormal	xx (xx.xx)
If Abnormal	
Abnormal CS	xx (xx.xx)
Abnormal NCS	xx (xx.xx)
Thyroid	
Normal	xx (xx.xx)

Document Title:	Document ID:	BP04-01
Statistical Analysis Plan	Version Number:	3.1
	Effective Date:	25-Nov-2021

Abnormal	xx (xx.xx)
If Abnormal	
Abnormal CS	xx (xx.xx)
Abnormal NCS	xx (xx.xx)
Musculoskeletal System	
Normal	xx (xx.xx)
Abnormal	xx (xx.xx)
If Abnormal	
Abnormal CS	xx (xx.xx)
Abnormal NCS	xx (xx.xx)
Neurological System	
Normal	xx (xx.xx)
Abnormal	xx (xx.xx)
If Abnormal	
Abnormal CS	xx (xx.xx)
Abnormal NCS	xx (xx.xx)
Other	
Normal	xx (xx.xx)
Abnormal	xx (xx.xx)
If Abnormal	
Abnormal CS	xx (xx.xx)
Abnormal NCS	xx (xx.xx)

- The Capital "N" in the column header represents the total number of patients in Safety Analysis Set.
- The small "n" in summary statistics represents the total number of patients.
- All Percentages rows are based on the total number of Safety Analysis Set.
- Programmer note: Visit x: Screening Visit, Visit 1, Visit 2, Visit 3, Visit 4 and Visit 5.
- Source: Listing 16.3.6

Document Title:	Document ID:	BP04-01
Statistical Analysis Plan	Version Number:	3.1
	Effective Date:	25-Nov-2021

Table 14.3.6.1. Summary of Serum Pregnancy Test (Safety Analysis Set)

	N = xx

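### SAP Table 14.3.3 measures vital-sign change from Screening and tests the pre-dose Day 1 reading as a change, although the protocol's baseline is the last value before first dose (minor correction)

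*SAP*

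**What the plan says.** **Baseline rule.** Protocol 9.4.1 states: "The last measurement prior to first dose of study treatment will serve as the baseline measurement". The synopsis repeats it under Statistical Methods.

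**Schedule and timing.** Protocol Table 1 schedules vital signs at Screening (up to 14 days before Day 1), on Day 1 and at Weeks 4, 8, 16 and 24. It numbers Day 1 as Visit 1 and leaves Screening without a number. Footnote d says: "The vital signs (pulse, blood pressure, respiration rate, and body temperature) will be taken before benralizumab administration". Protocol 8.1.2 agrees: "The vital signs will be taken before benralizumab administration, and, if possible, blood drawing and usual asthma controller medication".

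**SAP text.** SAP 6.3.1 asks for actual values and change from baseline at each visit, with a paired t-test or Wilcoxon signed-rank test at the 5% level. It gives a formula for change but never says which measurement is the baseline. SAP 5.1, which otherwise follows the protocol's general considerations, omits the baseline sentence.

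**SAP table shell.** Table 14.3.3 carries the title "Analysis of change in Vital Sign parameters from baseline to Visit 1, Visit 2, Visit 3, Visit 4 and Visit 5". Its reference row is headed "Baseline (Screening Visit", with the bracket closing there. Its footnote defines "Change from Baseline= Post-Baseline – Baseline", and its instruction to the programmer is "Programmer Note: Visit x: Visit 1, Visit 2, Visit 3, Visit 4 and Visit 5". Each of those visits has a p-value cell under change and another under percentage change, from a paired t-test.

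**The concern.** The shell and the protocol name different baselines for the same measurement. Under the protocol rule, a Day 1 reading taken before dosing is the baseline itself. The shell treats it as the first post-baseline value.

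This has two consequences for the printed table. The Visit 1 rows would show changes and p-values for a visit at which no drug had yet been given. The Visit 2 to 5 rows would show changes from a reading that is not the protocol's baseline whenever a later pre-dose reading exists.

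Safety is the primary objective, so a reader of the report may take a table of vital-sign changes with p-values as evidence about the drug. For the Visit 1 rows it cannot be.

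**Working it through.** The plan states no figure on this point. The check compares the two documents and then counts the table's cells.

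**Step 1. Is Visit 1 the same as Screening?** No.
- Protocol Table 1 numbers Day 1 as Visit 1.
- SAP Table 14.3.5 lists the two separately: "Programmer note: Visit x: Screening Visit, Visit 1, Visit 2, Visit 3, Visit 4 and Visit 5".
- SAP Table 14.1.6 reports study drug given at Visit 1.
- SAP Table 14.2.1.1 does place history items under Visit 1, so the labels are not perfectly tidy. That does not rescue the row. If Visit 1 were Screening, every Visit 1 change would be exactly zero and the paired t-test undefined.

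**Step 2. Which reading is the protocol baseline for vital signs?**
- Scheduled readings before first dose: Screening and Day 1.
- The later of the two is Day 1, provided it was recorded before dosing, as footnote d and section 8.1.2 require. In section 8.1.2 the words about possibility qualify the order relative to blood drawing and controller medication, not relative to dosing.
- If there is no such Day 1 reading, Screening is the protocol baseline.

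**Step 3. Which comparisons are affected?**

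Inputs: 5 parameters (pulse rate, respiratory rate, systolic pressure, diastolic pressure, temperature; SAP 6.3.1 and Table 14.3.3), 5 visits (programmer note), and 2 columns with p-values (change, percentage change).

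| Item | Comparisons | P-value cells |
|---|---|---|
| Table as drafted | 5 × 5 = 25 | 25 × 2 = 50 |
| Visit 1: one pre-dose reading against another | 5 × 1 = 5 | 5 × 2 = 10 |
| Share of table | 5/25 = 20% | 10/50 = 20% |
| Visits 2 to 5: not the protocol baseline where a Day 1 pre-dose reading exists | 5 × 4 = 20 | 20 × 2 = 40 |
| Table after correction | 20 | 40 |

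**Step 4. Does the same conflict arise elsewhere?** The scheduled data do not create it. Protocol Table 1 has no Day 1 eosinophil count, and protocol 8.1.3 places the safety laboratory tests at Screening and end of study. For those measures Screening is the only scheduled pre-dose value, so the Screening label in the eosinophil table (14.2.3) agrees with the protocol rule. The shells of the haematology and biochemistry tables (14.3.2.1 and 14.3.2.2) are not in the text available, so for them this rests on the schedule alone.

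**The case against.** The strongest reply is precedence. SAP section 1 says that differences described in the SAP override the protocol, and the mock tables are part of the SAP. The row label, title, programmer note and table lists are consistent with one another, and the eosinophil table uses the same label. Screening could therefore be a deliberate convention. Under it Visit 1 does follow baseline, and both documents ask for change at each visit.

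Part of this stands: the shell is SAP text, and the choice may have been intended. But the same clause says that changes from the protocol are detailed in the SAP, and no section states or explains a new baseline rule. A row label is weak evidence of a decision. Even a deliberate Screening baseline would leave a Visit 1 test comparing two untreated readings. The request for change at each visit has to be read with the baseline rule, because a baseline visit has no change from itself.

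The second reply is that little is at stake. Both readings are untreated and at most 14 days apart, and the shell prints observed values at Screening and at every visit, so a reader can compare Day 1 with later visits directly. This stands in full and sets the weight of the point.

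A reader might go further and infer that the Visit 2 to 5 changes are biased, or that the table will produce false signals at a calculable rate. The documents support neither. They give no data on any shift between Screening and Day 1, and a false-positive rate would need an assumption about dependence among the five parameters, two of which are systolic and diastolic pressure.

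**Conclusion.** The inconsistency is real and minor. Followed as written, Table 14.3.3 gives 5 of 25 comparisons (10 of 50 p-value cells) that say nothing about treatment. The remaining 20 (40 cells) depart from the protocol's baseline for every patient with a Day 1 pre-dose reading.

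This rests on two assumptions: that Visit 1 means Day 1 throughout Table 14.3.3, and that sites follow the protocol's timing rule.

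It would be wrong to conclude that the primary safety results are compromised. Vital-sign change is not among the endpoints listed in SAP 6.1.1 and 6.1.2. Adverse event percentages, their confidence intervals and the sample size do not depend on this table. It would also be wrong to conclude that every Screening-labelled baseline in the SAP is an error: for eosinophils the schedule makes Screening the right value.

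**What to change.** 1. Add the protocol's baseline sentence to SAP 5.1, applying to all change-from-baseline tables. Where Screening is the only pre-dose value, as scheduled for eosinophils and laboratory tests, it is the baseline under that same rule and needs no exception.
2. In Table 14.3.3, define baseline by one rule. Use the Visit 1 reading, treated as pre-dose under the protocol's timing requirement. Use Screening only if the Visit 1 reading is missing or a recorded deviation shows that it was taken after dosing.
3. Remove Visit 1 from the change and p-value rows, the title, the programmer note, the table of contents and the list of tables. Screening may stay as an observed-value row.

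**Cost.** One sentence in the SAP and one reprogrammed table. The pre-dose status of Day 1 readings rests on the protocol's timing rule: Listing 16.3.4 shows no date or time for vital signs, so the order cannot be checked from it against the dosing times in Listing 16.1.6.1. The footnote to Table 14.1.1.1 already reports disposition counts (154 enrolled or screened, 124 completed, 20 discontinued). The revision should therefore be documented as restoring the protocol's own rule, so that it is not taken for a choice made after seeing data.
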